2.3. Exploratory Objectives

Non-applicable.

2.4. Specification of endpoints

Primary Endpoint: The primary endpoint is at index consultation (day 0).

Secondary Endpoints: Secondary endpoints are days 0-21, 7, 28 and 60.

3. Study Design

3.1 Trial Design

The study is a pragmatic randomised controlled superiority trial, with a two-group parallel design and a participant allocation ratio of 1:1.

Control arm: Usual Care

Participants assigned to the control group will receive the GP's usual care of adults (≥ 18 years) presenting with symptoms of an acute LRTI where the GP suspects CAP. Usual care is recommended to follow applicable guidelines. Usual care does not include a FLUS examination.

Intervention arm: +FLUS

Participants assigned to the intervention group will receive a FLUS examination during the index consultation (day 0) in addition to usual care.

3.2. Randomization and Blinding

The unit of randomisation is the patient. Participants will be randomized 1:1 to either Usual Care or +FLUS group. Each general practitioner will be provided with a pile of sequentially numbered opaque sealed envelopes (SNOSE)¹⁹. The SNOSE piles will be prepared by a remote independent researcher, using permuted block randomization to ensure similar enrolment in both groups. Different block sizes will be used to prevent the allocation sequence from being anticipated. Details on block sizes and list lengths are unavailable to general practitioners who enroll patients and assign interventions.

Owing to the type of intervention, participants and GPs are not blinded. However, members of the research team involved in obtaining or analysing data (outcome assessors and data analysts) will be blinded to the allocation until data analyses have been finalised.

3.3. Sample Size

Based on previous audit projects in general practice in Denmark²⁰⁻²¹, a Danish study by Holm et al.⁹ and a Dutch study on reducing antibiotic prescribing in patients with LRTI²², we assume to detect a 15% decrease in antibiotic prescribing in patients with LRTI from 50% (usual care) to 35% (+FLUS). Using a 5% significance level and a power of 80% a total of 340 patients with 170 trial participants in each arm is needed. We assume withdrawal or discontinuation by a maximum of 10% of participants²². Furthermore, we increase the sample size by 5% to account for covariates in the analyses. Consequently, we plan to include a total of 390 trial participants (195 in each arm). Each GP is encouraged to include a minimum of 10 participants to account for the individual effect of FLUS on antibiotic prescribing at a GP level.

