4.2 Baseline characteristics

Patients

Date of enrolment, age, sex (provided from social security number), comorbidities, smoking status. Participants' symptoms and signs of acute LRTI, the results of physical examination and any POCT performed as part of usual care (e.g., CRP) in both groups. FLUS pathological findings will be reported for the +FLUS group.

General practitioners

Age, sex, region of Denmark, type of clinic, seniority as a GP, experience with POCUS, experience with FLUS, type of ultrasound device (hand-held, laptop or fixed), ultrasound brand and model, transducer(s) used, and baseline antibiotic prescribing.

Baseline characteristics	Unit/options	Endpoint (days from index consultation)					Type of data	Statistical analyses
		0	0-21	7	28	60		
General practitioners								

Age	Years	X				Ratio	Mean/Median, 95% CI
Sex	Male/Female	X				Nominal	Proportions
Region of Denmark	North/Central/Southern /Zealand/Capitol	X				Nominal	Proportions
Type of clinic	Solo/Partnership/ Collaboration/Other	X				Nominal	Proportions
Seniority as a GP	Years	X				Ratio	Mean/Median, 95% CI
Experience POCUS	Years	X				Ratio	Mean/Median, 95% CI
Experience FLUS	Years	X				Ratio	Mean/Median, 95% CI
Type of ultrasound machine system	Hand-held, Laptop, Stationary	X				Nominal	Proportions
Number of transducers available	Number	X				Ratio	Mean/Median, 95% CI
Type of transducer used for FLUS	Linear/curved/phased-array/other	X				Nominal	Proportions
Baseline antibiotic prescribing	Defined as daily doses per 1000 patients per year	X				Ratio	Mean/Median, 95% CI
Patients							
Date of enrolment	Date	X				Ordinal	Used to calculate age at date of enrolment
Date of birth	Date	X				Ordinal	Used to calculate age at date of enrolment
Age	Years	X				Ratio	Mean/Median, 95% CI, Independent samples t-test/Mann Whitney U
Sex	Male/Female	X				Nominal	Proportions, Chi ² or Fischer's exact
List of comorbidities	Present/not present	X				Nominal	Proportions, Chi ² or Fischer's exact
Smoking status	Smoker/former smoker/never-smoker	X				Nominal	Proportions, Chi ² or Fischer's exact
List of symptoms	Present/not present	X				Nominal	Proportions, Chi ² or Fischer's exact
List of clinical findings	Present/not present	X				Nominal	Proportions, Chi ² or Fischer's exact
List of point-of-care tests	Performed/not performed	X				Nominal	Proportions, Chi ² or Fischer's exact

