5.4. Primary Outcome

The primary outcome data will be displayed in a 2x2 table comparing the dichotomous outcome variable of antibiotics prescribed at the index consultation. The primary analyses will be the proportion of patients prescribed an antibiotic at the index consultation (day 0) in the two groups. The primary analyses will also include the risk ratio (RR) presented with a 95% confidence interval (95% CI). We will test if there is a difference in the risk of having antibiotics prescribed at the index consultation between the two groups. We will consider the variation between GPs as part of the primary analyses.

Outcome	Unit/options	Endpoint (days from index consultation)	Type of data	Statistical analyses
---------	--------------	---	--------------	----------------------

		0	0-21	7	28	60		
Primary outcome								
Antibiotics prescribed at index consultation	Yes/No	X					Nominal	Proportions, RR, 95% CI, Chi ²

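### The sample size allows 5% for covariates and section 5.4 promises to consider GP variation, but the only primary analysis listed is a 2x2 chi-square with RR that uses neither

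*SAP*

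**What the plan says.** Section 3.3 sizes the trial for a fall in prescribing "from 50% (usual care) to 35% (+FLUS") and concludes that "a total of 340 patients with 170 trial participants in each arm is needed". It then makes two additions. The first is for loss: "We assume withdrawal or discontinuation by a maximum of 10% of participants". The second is for modelling: "we increase the sample size by 5% to account for covariates in the analyses". The result is "we plan to include a total of 390 trial participants (195 in each arm"). The section also encourages each GP to recruit at least 10 patients, so that GP-level effects can be taken into account.

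Section 5.4 opens with "The primary outcome data will be displayed in a 2x2 table comparing the dichotomous outcome variable of antibiotics prescribed at the index consultation". It adds a risk ratio with its 95% CI and a test of the difference. It ends by saying that between-GP variation will be considered in the primary analyses, without giving a method. The table beneath it lists a chi-square test next to the proportions, RR and CI, and nothing else.

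Section 4.2 lists the patient data collected at baseline, beginning "Date of enrolment, age, sex (provided from social security number), comorbidities, smoking status". No section names any of these as an adjustment variable. Section 5.1 mentions the bootstrap only for non-normality, and section 5.6 lists subgroups, not model covariates.

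**The concern.** The trial was enlarged for a kind of analysis that the plan does not describe. Two things follow.

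First, the primary analysis is not fixed. Section 5 declares everything defined in the protocol or the SAP to be a priori. On the SAP's wording, a plain chi-square, a GP-adjusted model and a model with some set of baseline covariates could each be presented as planned. They can give different RRs, intervals and p-values for the comparison that carries the conclusion.

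Second, the method actually listed leaves information unused. Under section 3.2 every GP has a separate pile of envelopes prepared with permuted blocks. If blocks run within piles, allocation is balanced within GP. A pooled chi-square ignores that balance, so it is somewhat conservative when GPs differ in their prescribing habits. It also makes no use of patient characteristics that are recorded anyway and may predict prescribing.

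**Working it through.** **1. The plan's own figure.** Inputs from section 3.3: 50% and 35%, significance level 5%, power 80%. The SAP does not state sidedness; two-sided reproduces its figure. With the pooled-variance formula and mean proportion 0.425:

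n per arm = [1.960 × √(2 × 0.425 × 0.575) + 0.842 × √(0.50 × 0.50 + 0.35 × 0.65)]² / 0.15² = (1.370 + 0.582)² / 0.0225 ≈ 169.3, rounded up to 170, or 340 in total. This matches exactly.

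**2. Is the 5% really in the 390?**
- Dropout alone: 340 × 1.10 = 374, or 340 / 0.90 = 378.
- Dropout and covariates: 340 × 1.15 = 391, or 340 × 1.10 × 1.05 = 392.7.

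Only the second pair comes close to 390, so the covariate allowance is part of the planned number. It amounts to 340 × 0.05 = 17 patients.

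**3. What those 17 patients do under the listed chi-square.** Power at 170 per arm is 80.2%. At 340 × 1.05 = 357 patients (178.5 per arm) it is about 82%.

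**4. What patient-level adjustment could add.** The SAP gives no R-squared, so the values below are assumptions. If covariates explain a share R² of the outcome variance, the effective size per arm is roughly n / (1 − R²). Power for 50% against 35%:

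| Assumed R² | 170 per arm | 195 per arm |
|---|---|---|
| 0 | 80.2% | 85.3% |
| 2% | 81.0% | 86.0% |
| 5% | 82.1% | 87.0% |
| 10% | 84.1% | 88.7% |
| 15% | 86.1% | 90.4% |

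The gain is about 0.8 to 6 points at 170 per arm and 0.7 to 5 points at 195 per arm. The 195 column is closer to section 5.1, which analyses all participants, and to section 5.2, which counts an unresolved missing primary outcome as a prescription.

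**5. What accounting for GP could add.** The SAP gives no ICC, so this too is a range. Simulation with 39 GPs of 10 patients each, split 5:5 within GP (assumed), logit-normal GP effects and 20,000 replicates, comparing the plain chi-square with a Cochran-Mantel-Haenszel test stratified by GP:

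| Assumed latent-scale ICC | Chi-square type I error | Chi-square power | Stratified type I error | Stratified power |
|---|---|---|---|---|
| 0 | 4.6% | 85.1% | 4.7% | 85.3% |
| 0.05 | 4.4% | 85.4% | 5.0% | 86.5% |
| 0.10 | 4.1% | 85.3% | 5.2% | 87.2% |
| 0.20 | 3.3% | 86.6% | 5.2% | 90.0% |

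The chi-square's type I error stays below 5% and falls as GPs differ more. For ICCs of 0.05 to 0.20, stratifying restores it to about 5% and adds about 1 to 3 power points.

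**The case against.** The strongest reply is that the SAP does not choose an unadjusted primary analysis. The 2x2 table is described as a display, and the same paragraph commits to considering GP variation. GP may be one of the covariates behind the 5%. Section 3.3 speaks of covariates in the analyses generally, not in the primary analysis, and the protocol, which is not at hand, may define more. This stands to the extent that 3.3 and 5.4 do not make flatly opposite statements. It does not remove the gap. The SAP is where the primary model should be named, and its table lists a test that cannot take GP into account.

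A reader might infer that the extra 5% is wasted. It is not: those patients enter the chi-square and raise its power by about 2 points.

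A reader might also infer that the trial is underpowered or that chance imbalance biases the result. Neither follows. The 340 reproduces exactly, and an unadjusted comparison of randomised arms is valid.

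Finally, the gains in precision rest on assumed values. Nothing in the SAP shows how strongly age, comorbidity or smoking predicts a GP's decision to prescribe, and with weak predictors the gain would be negligible. That also stands, and is why only ranges are given.

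**Conclusion.** The mismatch is real. A covariate allowance is built into the 390 and GP variation is promised a place in the primary analyses, while the one analysis listed uses neither GP nor any covariate. The consequences are an incompletely specified primary analysis and a loss of efficiency, not a loss of validity.

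The size is modest: about 0.7 to 5 power points at 195 per arm, or 0.8 to 6 at 170 per arm, for an assumed R-squared of 2% to 15%. Accounting for GP would separately be worth about 1 to 3 points for an assumed ICC of 0.05 to 0.20, provided blocks run within each GP's pile. The documents do not support the stronger statement that the trial pays for covariates and gets nothing in return.

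**What to change.** - **Section 5.4 and its table:** name one primary model for antibiotic prescription at day 0, with arm, GP (as random intercept or as stratum) and a short fixed list of patient variables already collected, for example age, pulmonary comorbidity and smoking status. This list is a suggestion; the trial team should choose it. Use only variables determined before allocation. Report a marginal RR with 95% CI, for example by standardising a logistic model, so that the effect measure stays the one the SAP names.
- **Supportive analysis:** keep the 2x2 table and chi-square, labelled as unadjusted.
- **Fallback:** state what replaces the model if it does not converge, for example the Mantel-Haenszel RR stratified by GP. GPs with patients in only one arm contribute nothing to that estimate, so the rule should say how they are handled.
- **Section 3.3:** say which covariates the 5% refers to, or remove that rationale. The planned 390 need not change.

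The cost is a new SAP version, which section 6 already provides for, and a few lines of code. The downside is that the covariates and the fallback must be fixed before unblinding.

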3.4 Statistical interim analyses

No interim analysis will be performed.

3.5 Timing of final analysis

All outcomes will be analysed collectively.

4. Trial Population

4.1. Eligibility

Patients

Inclusion criteria:

Patients aged ≥ 18 years with acute cough (< 28 days) and at least one other symptom of LRTI and where the GP suspects a community-acquired pneumonia (CAP).

Exclusion criteria:

- Previous antibiotic treatment for the current episode of acute LRTI.
- The patient is not listed with the GP (no medical record available).
- The patient is not capable of understanding and signing informed consent.
- The patient do not wish to participate in the study.

General practitioners

Inclusion criteria:

General practitioners who use point-of-care ultrasonography at least once a week in general practice or out-of-hour services.

4.2 Baseline characteristics

Patients

Date of enrolment, age, sex (provided from social security number), comorbidities, smoking status. Participants' symptoms and signs of acute LRTI, the results of physical examination and any POCT performed as part of usual care (e.g., CRP) in both groups. FLUS pathological findings will be reported for the +FLUS group.

General practitioners

Age, sex, region of Denmark, type of clinic, seniority as a GP, experience with POCUS, experience with FLUS, type of ultrasound device (hand-held, laptop or fixed), ultrasound brand and model, transducer(s) used, and baseline antibiotic prescribing.

Baseline characteristics	Unit/options	Endpoint (days from index consultation)					Type of data	Statistical analyses
		0	0-21	7	28	60		
General practitioners								

Age	Years	X				Ratio	Mean/Median, 95% CI
Sex	Male/Female	X				Nominal	Proportions
Region of Denmark	North/Central/Southern /Zealand/Capitol	X				Nominal	Proportions
Type of clinic	Solo/Partnership/ Collaboration/Other	X				Nominal	Proportions
Seniority as a GP	Years	X				Ratio	Mean/Median, 95% CI
Experience POCUS	Years	X				Ratio	Mean/Median, 95% CI
Experience FLUS	Years	X				Ratio	Mean/Median, 95% CI
Type of ultrasound machine system	Hand-held, Laptop, Stationary	X				Nominal	Proportions
Number of transducers available	Number	X				Ratio	Mean/Median, 95% CI
Type of transducer used for FLUS	Linear/curved/phased-array/other	X				Nominal	Proportions
Baseline antibiotic prescribing	Defined as daily doses per 1000 patients per year	X				Ratio	Mean/Median, 95% CI
Patients							
Date of enrolment	Date	X				Ordinal	Used to calculate age at date of enrolment
Date of birth	Date	X				Ordinal	Used to calculate age at date of enrolment
Age	Years	X				Ratio	Mean/Median, 95% CI, Independent samples t-test/Mann Whitney U
Sex	Male/Female	X				Nominal	Proportions, Chi ² or Fischer's exact
List of comorbidities	Present/not present	X				Nominal	Proportions, Chi ² or Fischer's exact
Smoking status	Smoker/former smoker/never-smoker	X				Nominal	Proportions, Chi ² or Fischer's exact
List of symptoms	Present/not present	X				Nominal	Proportions, Chi ² or Fischer's exact
List of clinical findings	Present/not present	X				Nominal	Proportions, Chi ² or Fischer's exact
List of point-of-care tests	Performed/not performed	X				Nominal	Proportions, Chi ² or Fischer's exact
Point-of-care test results	CRP: mg/L; Leukocytes: 10 ⁹ /L; Saturation: %; Pulse: Beats/min.	X				Ratio	Mean/Median, 95% CI, Independent samples t-test/Mann Whitney U

5. Statistical Principles and Analysis

All analyses described in this plan are considered *a priori* analyses as they have been defined in the protocol or in this statistical analysis plan. If any *post-hoc* analyses are conducted, they will be defined as such in the report.

5.1. Analysis set

Analyses will be performed as intention to treat (ITT) (pragmatic trial). The primary analysis population will comprise all participants, irrespective of follow-up. We will use bootstrap to handle non-normality and use a 5% significance level.

5.2. Lost to follow-up and missing data

In the case of missing data on the primary endpoint, the GP who enrolled the participant will be contacted to clarify if antibiotics were prescribed at the index consultation. If clarification is not obtained, we will consider it as if antibiotics were prescribed at the index consultation. We expect that the use of an e-CRF for GPs to complete at the time of index consultation will keep missing data on the primary outcome at a minimum. We expect that only observed data will be included in the secondary analyses.

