As standard care and communication method, data on changes in medicine or new prescriptions are automatically uploaded to participants' electronic shared medication record (FMK). We will review the participants' shared medication records (FMK) for outcomes on antibiotics prescribed during follow-up:

- 2.1) Proportion of participants who have antibiotics prescribed within 7 days after the index consultation.
- 2.2) Proportion of participants who have antibiotics prescribed within 28 days after the index consultation.
- 2.3) Proportion of antibiotics prescribed as delayed antibiotic prescriptions at index consultation (day 0).

As standard care and communication, GPs receive notices of health-related events, e.g., discharge and out-of-hour notices. From participants' electronic medical records, we will obtain outcomes on the clinical course during follow-up:

3) Outcomes from participants' electronic medical records:

- 3.1) Proportion of participants with reconsultations, defined as any primary care contact (general practice or out-of-hour services), within 28 days after the index consultation.
- 3.2) Proportion of participants admitted to the hospital within 28 days after the index consultation.

- 3.3) Proportion of participants with complications (pleural infection (defined as complicated parapneumonic effusion or empyema), lung abscess, or sepsis) during admission to hospital within 28 days after the index consultation.
- 3.4) Proportion of participants with imaging other than FLUS (any imaging performed in secondary health care services) performed within 28 days after the index consultation.
- 3.5) Other imaging methods performed within 28 days after the index consultation.
- 3.6) Proportion of participants referred with suspicion of cancer within 60 days after the index consultation.
- 3.7) Proportion of participants diagnosed with cancer within 60 days after the index consultation.
- 3.8) Number of spontaneously reported unintended events up to 60 days after the index consultation.
- 3.9) All-cause mortality up until day 28 and day 60.

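### Day-0 outcomes still missing after the GP query are scored as prescribed, with no check of FMK first and no sensitivity analysis of the rule

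*SAP*

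**What the plan says.** SAP section 5.2 handles a missing primary outcome in two steps. The enrolling GP is asked whether antibiotics were prescribed; failing an answer, "If clarification is not obtained, we will consider it as if antibiotics were prescribed at the index consultation". The rule is the same in both arms. The section expects that the e-CRF completed at the consultation "will keep missing data on the primary outcome at a minimum", but gives no rate.

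Section 5.1 fixes who is analysed: "The primary analysis population will comprise all participants, irrespective of follow-up". Section 5.4 then reports proportions, an RR with 95% CI and a chi-squared test, so the assumed events count in each.

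Section 2.2 describes a second source. For FMK it says that "data on changes in medicine or new prescriptions are automatically uploaded", and it plans to use that record: "We will review the participants' shared medication records (FMK) for outcomes on antibiotics prescribed during follow-up". Section 5.2 does not mention FMK.

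No section tests the rule. Section 5.3 commits to looking for missing values, and section 5.6 lists subgroup analyses only.

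**The concern.** The rule is single imputation of the only primary outcome. Whenever the true answer was no prescription, it creates a false event. The plan would therefore assume a value that a record already opened by the trial might often supply.

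The direction of the resulting bias depends on how unresolved cases split between the arms. The GP who fills in the form and answers the query knows the allocation (section 3.2: "Owing to the type of intervention, participants and GPs are not blinded"), so a difference by arm is possible, though nothing in the SAP shows that one is likely. The SAP does not promise counts by arm or an alternative analysis. Under the introduction to section 5, a check added later would be labelled post hoc.

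**Working it through.** **Inputs.** Section 3.3 gives 195 per arm, a 5% significance level, and antibiotic prescribing falling "from 50% (usual care) to 35% (+FLUS"). The SAP gives no missingness rate, so every rate m below is an assumption. Missingness is taken as unrelated to the true outcome within each arm. Power is for a two-sided pooled-variance comparison of two proportions (normal approximation), ignoring variation between GPs.

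**The plan's own figure.** With a mean proportion of 0.425:

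n = [1.96·√(2·0.425·0.575) + 0.8416·√(0.50·0.50 + 0.35·0.65)]² / 0.15² = 169.3, rounded up to 170 per arm. This reproduces the stated 340. At 195 per arm, power is 85.3%.

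**What the rule does.** With true proportion p and unresolved share m, the analysed proportion is

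p_obs = p(1 − m) + m = p + m(1 − p),

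so each arm gains 195·m·(1 − p) false events. At m = 5% that is 195·0.05·0.50 = 4.88 in usual care and 195·0.05·0.65 = 6.34 in +FLUS.

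**Planned effect (50% versus 35%):**

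| Unresolved, usual care / +FLUS | Analysed proportions | RR | Power |
|---|---|---|---|
| 0 / 0 | 0.500, 0.350 | 0.700 | 85.3% |
| 2% / 2% | 0.510, 0.363 | 0.712 | 83.6% |
| 5% / 5% | 0.525, 0.3825 | 0.729 | 80.9% |
| 5% / 4% | 0.525, 0.376 | 0.716 | 84.3% |
| 5% / 3% | 0.525, 0.3695 | 0.704 | 87.3% |
| 2% / 0 | 0.510, 0.350 | 0.686 | 89.4% |
| 0 / 2% | 0.500, 0.363 | 0.726 | 78.2% |
| 5% / 0 | 0.525, 0.350 | 0.667 | 93.9% |
| 0 / 5% | 0.500, 0.3825 | 0.765 | 64.8% |

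With equal missingness, power falls below 80% only above about 6% per arm (0.060 × 390 ≈ 23 participants).

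**When the RR is exaggerated.** The RR is unchanged when m_FLUS/m_usual = [0.35/0.65] × [0.50/0.50] = 0.54. Below that ratio the rule favours FLUS; above it the RR is diluted. The test has a different crossover: at 5% in usual care, power is back to 85.3% when +FLUS has 3.70% unresolved, a ratio of 0.74. Between the two ratios the RR is diluted while the chance of significance rises, as in the 5% / 3% row.

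**No true effect (50% in both arms):**

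| Unresolved, usual care / +FLUS | RR | Rejection rate |
|---|---|---|
| equal | 1.000 | 5.0% |
| 5% / 4% | 0.990 | 5.1% |
| 2% / 0 | 0.980 | 5.4% |
| 5% / 0 | 0.952 | 7.8% |

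**What extreme-case bounds would show.** At 2% per arm, the RR ranges from 0.343/0.510 = 0.673 to 0.363/0.490 = 0.741. At 5% per arm, it ranges from 0.3325/0.525 = 0.633 to 0.3825/0.475 = 0.805.

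**The case against.** The rule is complete, set in advance, identical in both arms and consistent with the analysis set. With a true effect and equal missingness it is conservative; with no effect and equal missingness it is unbiased. Unresolved cases should be rare. The outcome is the GP's own decision, recorded at the consultation, and section 4.1 excludes patients for whom the GP holds no record ("The patient is not listed with the GP (no medical record available")). A case stays unresolved only if the form is blank and the query also fails. The larger shifts above need about 10 such cases in one arm (0.05 × 195 = 9.75) and none in the other.

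FMK is also an imperfect source. The SAP does not say that it identifies the consultation or indication behind a prescription, or how delayed prescriptions appear in it. And if the report gave unresolved counts by arm, a reader could bound the effect by hand.

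Most of this stands. It limits the size of the problem and is the reason to keep the GP query. It does not make the rule checkable: the rule is conservative only for certain splits between arms, and the SAP does not commit to reporting the split.

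**Conclusion.** The point holds and should be fixed, as a cheap safeguard; it does not threaten the trial. An unresolved outcome becomes an assumed event in the primary RR and test, without a look at a record the trial already uses and without any planned check.

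At the low missingness the SAP expects, the effect is small: an RR of 0.712 instead of 0.700 at 2% per arm, and 0.686 to 0.726 if 2% is unresolved in one arm only. It becomes material only with several percent unresolved and a marked imbalance. These sizes rest on assumed missingness rates, on missingness unrelated to outcome within arm, and on a calculation that ignores variation between GPs.

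**What to change.** Keep the rule for whatever remains unresolved, and reword section 5.2 along these lines:

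> A missing day-0 outcome will be resolved by GP clarification together with a check of FMK for an antibiotic prescription dated day 0, before any imputation. An outcome that remains unresolved will be counted as prescribed. The numbers missing, recovered (by source) and unresolved will be reported by arm. Sensitivity analyses of the primary RR will be: (a) observed cases only; (b) unresolved counted as prescribed in +FLUS and not prescribed in usual care; (c) the reverse of (b).

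All participants stay in the intention-to-treat set, and the primary analysis stays fixed in advance. The cost is a change of SAP wording, a small look-up and three extra analysis runs, with no more patients. An FMK entry may occasionally concern another indication or come from another prescriber, so GP clarification remains part of the procedure.

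### The SAP names only the unblinded GP's e-CRF entry as source for the primary outcome, and does not use the automatic medication record (FMK) as a day-0 check or fallback

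*SAP*

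**What the plan says.** - **Primary outcome.** Sections 2.1 and 5.4 define it as a yes/no antibiotic prescription at the index consultation on day 0. Neither names a data source.
- **Source.** Section 5.2 expects few missing values because of the "use of an e-CRF for GPs to complete at the time of index consultation". This is the only place where the SAP says how the day-0 outcome is captured.
- **Missing values.** First, "the GP who enrolled the participant will be contacted to clarify if antibiotics were prescribed at the index consultation". Then: "If clarification is not obtained, we will consider it as if antibiotics were prescribed at the index consultation". FMK appears at neither step.
- **Blinding.** Section 3.2: "Owing to the type of intervention, participants and GPs are not blinded". The blinding of assessors in the same section covers members of the research team who obtain or analyse data.
- **FMK.** Section 2.2 says that "data on changes in medicine or new prescriptions are automatically uploaded to" the participant's shared medication record. It plans to review that record "for outcomes on antibiotics prescribed during follow-up", and lists outcomes 2.1 (7 days) and 2.2 (28 days). The same list has one day-0 item, outcome 2.3 on delayed prescriptions. Its heading covers both FMK and type of prescription, and the SAP does not say which of the two feeds 2.3.
- **Data checks.** Section 5.3 provides for examination of missing, outlying and unexpected values. It has no rule for an e-CRF entry that disagrees with FMK.

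**The concern.** The GP whose prescribing is under test also records the result and knows the allocation. Blinding the research team does not protect an entry made by someone outside it. An entry can be present, plausible and wrong: a prescription issued after the form was closed, a delayed prescription not counted, a slip in a yes/no field. Checks for missing or extreme values do not find such an error, and analysis by intention to treat does not correct it.

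The trial will also hold a second record of prescribing for the same participants. If the e-CRF says No and FMK shows an antibiotic on the index date, the SAP does not say what happens. A choice made after the data are seen would make the primary data set post hoc. The gap is plainest for missing entries: a participant can be counted as prescribed without anyone looking in a record that may show otherwise.

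**Working it through.** **Step 1. Sources side by side**

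| Outcome | Source named in the SAP | Check or fallback named |
|---|---|---|
| Primary, day 0 | GP's e-CRF (5.2) | Query to the same GP, then counted as prescribed |
| 2.1, within 7 days | FMK (2.2) | None needed for this point |
| 2.2, within 28 days | FMK (2.2) | None needed for this point |
| 2.3, delayed, day 0 | FMK or type of prescription; not clear | None |

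The two follow-up antibiotic outcomes have an automatic record behind them. None is named for the primary outcome.

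**Step 2. The plan's own figure**

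Inputs from 3.3: 50% v 35%, 5% level, 80% power. Taking the level as two-sided, without continuity correction, with p̄ = 0.425:

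n = [1.960·√(2·0.425·0.575) + 0.8416·√(0.50·0.50 + 0.35·0.65)]² / 0.15² = 169.3, so 170 per arm and 340 in total.

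This matches the SAP. The planned 390 is close to 340 × 1.15 = 391. The sample size is not at issue here, but it shows that the same normal approximation can be used below.

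**Step 3. One-sided illustration**

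Assumptions, not in the SAP: true prescribing is 50% in both arms, a share u of +FLUS prescriptions is not recorded, recording in the control arm is perfect, and there are 195 per arm. Then p₁ = 0.50 and p₂ = 0.50·(1 − u). With p̄ the mean of the two:

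P(significant, favouring FLUS) = Φ{ [(p₁ − p₂)·√195 − 1.960·√(2·p̄·(1 − p̄))] / √(p₁(1 − p₁) + p₂(1 − p₂)) }

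| u | p₂ | Expected entries lost (195 × 0.50 × u) | Argument of Φ | Probability |
|---|---|---|---|---|
| 0 | 0.500 | 0 | −1.960 | 2.5% |
| 2% | 0.490 | 2.0 | −1.763 | 3.9% |
| 5% | 0.475 | 4.9 | −1.467 | 7.1% |
| 10% | 0.450 | 9.8 | −0.973 | 16.5% |

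**Step 4. Equal under-recording**

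If the same share u is lost in both arms, the recorded risk ratio is p₂(1 − u) / [p₁(1 − u)] = p₂/p₁. It is unchanged. Under no true effect the two recorded proportions stay equal, and the probability stays at 2.5%. Only a difference between arms in recording creates a false effect.

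**Step 5. Near the threshold**

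Uncorrected chi-square: 98/195 v 79/195 gives p = 0.053; 98/195 v 78/195 gives p = 0.042. Any binary endpoint of this size has this property. It shows only that a few wrong entries can matter when the result is close.

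**The case against.** **The source is inferred.** The e-CRF is mentioned once, as a reason to expect few missing values. Source documents and verification are commonly left to the protocol, which is not at hand. This stands in part: a reader might infer that GP self-report alone decides the primary outcome for every participant, and the SAP does not say that. Unresolved missing values are imputed, and no passage excludes an FMK check. But 5.2 itself sets out what happens to a missing primary outcome, and it goes from the GP to imputation without FMK.

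**The FMK review is not cleanly confined to later days.** Outcome 2.3 is a day-0 item in the same list. This stands. It also means that a look at day 0 may be a small step from what is planned.

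**The entry is a sound source.** A yes/no act, recorded at the time by the person who performed it, is defensible in a pragmatic trial. FMK is not shown to separate the index consultation from another contact on the same day. This stands against replacing the e-CRF by FMK. It does not stand against using FMK as a check.

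**No differential error is shown.** The usual slips have no stated reason to differ by arm, and Step 3 takes the worst direction with perfect recording in the control arm. This stands, so the figures measure sensitivity and not likelihood.

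**Conclusion.** The point holds in limited form. For the primary outcome the SAP names only an unblinded GP's entry, a query to the same GP, and imputation as prescribed. It leaves an automatic record that the trial already plans to review out of both checking and fallback, and it has no rule for disagreement between the two.

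The size is unknown, because the SAP gives no rate of misrecording. Under the one-sided assumption of Step 3, the chance of a false significant reduction goes from 2.5% to between 3.9% and 16.5% for 2% to 10% under-recording in the +FLUS arm. Under equal proportional under-recording it does not change.

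Two stronger conclusions are not supported. One is that the primary result is biased: nothing in the SAP shows that recording errors are likely or that they differ by arm. The other is that FMK would make the outcome objective: the unblinded GP also makes the prescribing decision, and no record source removes that influence. The point is worth acting on because the remedy is cheap, not because an error has been shown.

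**What to change.** In sections 5.2 and 5.4, state that:

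1. Every participant's day-0 e-CRF entry, Yes and No alike, is checked against FMK for an antibiotic prescription dated day 0 from the index practice. The e-CRF is used to link that prescription to the index consultation.
2. FMK is consulted before a missing value is counted as prescribed.
3. Disagreements are resolved blind to arm, under a rule written before unblinding. The assessor should not see the FLUS findings, which 4.2 reports for the +FLUS group and which would reveal the allocation.
4. Agreement between e-CRF and FMK is reported by arm.
5. The result from e-CRF entries alone is given as a sensitivity analysis.

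The cost is SAP wording and a little extra work in a record review that is already planned. Prescriptions issued on the same day outside the index consultation have to be separated. The sample size does not change.
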